1 BACKGROUND AND STUDY RATIONALE

2 STUDY OBJECTIVES

The present study will be conducted to evaluate the efficacy and safety of AMG531 and to determine the recommended dose of AMG531 on the basis of its efficacy and safety when it is administered SC, QW at a dose of 1, 3, 6 or 10 µg/kg to the AA patients with immunosuppressive-therapy refractory thrombocytopenia and also to assess the pharmacokinetics of this product during the initial dose evaluation period. Its efficacy and safety during the extended period will also be evaluated. [REDACTED]

[figure not shown]
[REDACTED] - Efficacy and safety of AMG531 in the long term treatment beyond 1-year will be further evaluated for those showing continuous responses after 1 year treatment.

3 STUDY DESIGN

3.1 Study design

This is a multi-center, randomized, open-label, parallel, comparative, dose-finding study.

The overall study design is presented below.

3.2 Study phase

Phase 2

3.3 Study endpoints

3.3.1 Efficacy

3.3.1.1 Primary endpoint

The proportion of subjects achieving a platelet response at Week 9

3.3.1.2 Secondary endpoints

- The proportion of subjects achieving a platelet response any time during the initial dose evaluation period, Week1 through Week 12, Week 1 through Week 16, Week 1 through Week 24, and Week 1 through Week 52.
- The proportion of subjects who become platelet transfusion independent during the initial dose evaluation period, Week1 through Week 12, Week 1 through Week 16, Week 1 through Week 24, Week 1 through Week 52, Week 1 through Week 104, and Week1 through Week 156
- The proportion of subjects achieving erythroid response and/or neutrophil response during the initial dose evaluation period, Week1 through Week 12, Week 1 through Week 16, Week 1 through Week 24, Week 1 through Week 52, Week 1 through Week 104, and Week1 through Week 156
- Duration of platelet response
- Time to platelet response
- Changes in platelet count, hemoglobin concentration, and neutrophil count as continuous variables
- Changes in bone marrow cellularity and reticulin grade
- Changes in GIMEMA bleeding scale
- The proportion of subjects achieving tri-lineage responses
- The proportion of subjects able to discontinue study drugs after achieving normal level for 8 consecutive weeks without transfusion.
- Duration of study drug discontinuation while maintaining stable response

3.3.2 Pharmacokinetics

- Serum AMG531 concentration
- Pharmacokinetic parameters

3.3.3 Safety

- Adverse events
- Antibody formation against AMG531 and TPO

3.3.4 Exploratory

- The changes of primitive hematopoietic stem and progenitor cells
- The changes of progenitor cell pool (colony forming cell assay)
- The changes of stromal cell (colony forming unit fibroblast assay)
- Cytokine assay (IL-2, IL-6, IL-10, IL-12, IL-17, IFN- γ , TNF- α)

3.4 Randomization

Subjects assessed to be eligible for the study will be randomized to either of the four dose groups (1, 3, 6, or 10 $\mu\text{g}/\text{kg}$) according to a static allocation procedure using the baseline platelet count (platelet $\leq 10 \times 10^9/\text{L}$ or $10 \times 10^9/\text{L} < \text{platelet} \leq 30 \times 10^9/\text{L}$). A written procedure for randomization will be created and the details will be specified in it.

3.5 Target sample size

3.5.1 Efficacy and Safety

Eight in each cohort, a total of 32 subjects receiving AMG531 at a doses of 1, 3, 6 or 10 $\mu\text{g}/\text{kg}$ during the initial dose evaluation period will be assessed for the primary endpoint.

3.5.2 Pharmacokinetics

Serum concentrations of AMG531 will be determined in 3 in each cohort, a total of 12 subjects (in chronological order of enrollment) receiving AMG531 at a doses of 1, 3, 6 or 10 $\mu\text{g}/\text{kg}$.

4 INVESTIGATIONAL PRODUCT

4.1 Investigational product

- 1) Investigational Product: AMG531
- 2) Generic Name: Romiplostim
- 3) Content and Dosage Form: AMG531 is supplied in a single use glass vial as a sterile, white, preservative free, lyophilized powder. After reconstitution with 0.72 mL of sterile water for injection, AMG531 is available at a concentration of 0.5 mg/mL.

4.2 Labeling and packaging

4.2.1 Packaging

Each box contains 10 vials.

4.2.2 Labeling

Each label displays the following information. Color of outer carton and vial labels are designated to be white.

4.2.2.1 Label for outer cartons

Statements of “For clinical trial use only” and “Cannot be used for any other purposes except for clinical trial”, name and address of the IND holder, name of investigational product, batch number, expiration date and storage directions.

4.2.2.2 Label for vials

Statements of “For clinical trial use only”, name of investigational product and batch number, expiration date, and IND holder name.

4.3 Storage

To be stored at 2 to 8°C and protected from light.

4.4 Dispensing, storage, control and collection of investigational product

The sponsor will provide each investigative site with the investigational product after execution of the clinical study agreement. The sponsor will develop a written procedure for controlling the investigational product and deliver it to each investigative site.

The investigational product manager at each investigative site will properly store and control the investigational product according to the procedure, and will maintain records of the inventory, dispensing and return. He/she will properly check the quantity of the investigational product against the investigational product management record. In principle, the investigational product manager will return unused vials to the sponsor after study completion or at the delivery of a new batch. Partially used and empty vials will be destroyed at the site per site’s standard procedures.

The investigational product manager will submit a copy of the investigational product management record to the sponsor after study completion.

5 SELECTION OF SUBJECTS

5.1 Study subjects

Aplastic anemia (AA) subjects with thrombocytopenia refractory to immunosuppressive agents.

5.2 Inclusion criteria

Subjects may be included in the study if they meet all of the following criteria:

- 1) Patients who have provided written informed consent of their free will to participate in this clinical study. Written informed consent must be obtained prior to performing any study-related procedure
- 2) The subject is able and willing to comply with study procedures and follow-up as described in the protocol and ICF
- 3) Males and female subjects ≥ 19 years of age at the time of obtaining informed consent
- 4) Eastern Cooperative Oncology Group (ECOG) performance status (PS) score of ≤ 2 at the time of screening
- 5) Diagnosis of AA, confirmed by bone marrow and cytogenetic studies
- 6) Patient who is refractory to immunosuppressive therapy (IST)
- 7) Prior treatment with at least one course of horse or rabbit anti-thymocyte globulin (ATG) with cyclosporine
- 8) Thrombocytopenia defined as platelet $\leq 30 \times 10^9/L$
- 9) Fulfilling all of the following criteria in the screening examination
 - T-Bilirubin ≤ 1.5 times the upper limit of the laboratory normal range
 - ALT and AST ≤ 3 times the upper limit of the laboratory normal range
 - Creatinine ≤ 2.0 mg/dL

5.3 Exclusion criteria

Subjects must be excluded from participating in this study if they meet any of the following criteria:

- 1) Concurrent active infection not adequately responding to appropriate therapy
- 2) Human immunodeficiency virus positivity
- 3) Bone marrow reticulin grade of > 1 (Appendix 1)
- 4) Previous or concurrent active malignancies other than localized tumors diagnosed more than one year previously and treated surgically with curative intent (basal cell carcinoma or surgically resected in situ carcinoma of the cervix with apparent success ≥ 12 months prior to enrollment, as well as other cancers which have not been treated or have remained disease-free for at least 3 years before enrollment are eligible)
- 5) Clinically significant cardiac disease (class III or IV of the New York Heart Association (NYHA) classification; unstable angina pectoris, myocardial infarction within 6 months or is post angioplasty or stenting within 6 months; uncontrolled hypertension, clinically significant cardiac arrhythmia)
- 6) Arterial or venous thrombosis within the last 1 year before enrollment

- 7) Other cause of thrombocytopenia (for instance MDS, ITP, liver cirrhosis)
- 8) Subjects with AML or CMML
- 9) AA with hemolytic predominant PNH (hemolytic predominant is defined as LDH > 1.5 times the upper limit of the laboratory normal range)
- 10) Uncontrolled diabetes
- 11) Receiving other investigational agents within 16 weeks before starting the study treatment
- 12) Receiving any agent used to treat AA, including ATG or ATG+cyclosporine within 6 months before starting study treatment and/or cyclosporine or anabolic hormone within 6 weeks before starting the study treatment
- 13) History of PEG-rHuMGDF, recombinant human thrombopoietin, AMG531, and other TPO-receptor agonist
- 14) Who plans to conduct hematopoietic stem cell transplantation within 1 year
- 15) Known hypersensitivity to any recombinant *E. coli* derived product
- 16) Female subjects who are nursing or pregnant or are unwilling to take oral contraceptives or refrain from pregnancy if of childbearing potential
- 17) Subjects who are considered to be ineligible for the study by the investigator for reasons other than the above

5.4 Criteria for entering long-term treatment period

- 1) Subjects with platelet responses confirmed during 8 weeks prior to Week 53 (Week 46-Week 53)
- 2) Subjects who do not have any significant changes in medical condition during the initial evaluation period and extension period (Week 1-Week 52) including bone marrow stem cell disorders or new active malignancies

6 DOSING SCHEDULE AND CONCOMITANT THERAPY

6.1 Dose, dosing schedule, and treatment duration

There must be at least 3 days between the doses of AMG531 in each subject.

6.1.1 Initial-dose evaluation period (Week 1 to Week 8)

AMG531 will be administered at a dose of 1, 3, 6, or 10 µg/kg SC QW for 8 weeks. Dose adjustment (either escalation or reduction) will not be allowed during the initial dose evaluation period except for the cases defined in the 6.1.4 Criteria for discontinuing and resuming study treatment.

6.1.2 Extension period (Week 9 to Week 52)

Initial dose of AMG531 for the extension period will be decided based on the efficacy and safety data observed during the initial dose evaluation period. If a subject does not show a platelet response at Week 9, the dose will be increased by one level according to Table 6.1.2-1 AMG531 dose adjustment (extension period) table. If no platelet measurement is available due to the platelet transfusion, then that week's platelet response is considered as having no response.

6.1.2.1 Dose escalation

Dose escalation will be allowed during the extension period. If a subject does not show a platelet response after 4-week treatment with AMG531 at the previously escalated dose, the dose may be further increased by one level according to Table 6.1.2-1 at the discretion of the investigator, with the highest dose being 20 µg/kg. The necessity and timing of dose escalation after 4 week administration at a previously escalated dose will be decided by investigator after thorough consideration of the relevant safety and efficacy data for each subject.

6.1.2.2 Dose adjustment

If a subject shows a platelet response, the dose may be adjusted as appropriate to maintain the platelet response at the discretion of the investigator referring to the relevant efficacy and safety data of the each subject. For each dose adjustment, dose may be increased or decreased only by one level at a time according to the Table 6.1.2-1, with the highest dose being 20 µg/kg.

Table 6.1.2-1 AMG531 Dose adjustment table (extension period)

AMG531 Dose
1 µg/kg
3 µg/kg
6 µg/kg
10 µg/kg
13 µg/kg
16 µg/kg
20 µg/kg

6.1.3 Long-term treatment period (Week 53 to Week156)

6.1.3.1 Initial Dose

AMG531 will be administered SC QW at the same dose received as the last dose in the extension period. If dose adjustment is deemed to be necessary at Week 53 by investigator,

the dose may be adjusted according to the Table 6.1.3-1 Dose adjustment (long-term treatment period) table.

6.1.3.2 Dose adjustment

The dose may be adjusted as appropriate to maintain the platelet response at the discretion of the investigator. For each dose adjustment, dose may be increased or decreased only by one level at a time according to the Table 6.1.3-1, with the highest dose being 20 µg/kg and the lowest dose being 3 µg/kg.

Table 6.1.3-1 AMG531 Dose adjustment (long-term treatment period)

AMG531 Dose
3 µg/kg
6 µg/kg
10 µg/kg
13 µg/kg
16 µg/kg
20 µg/kg

6.1.3.3 Tapering and Discontinuation

If tri-lineage is maintained within normal level for 8-consecutive weeks with the same dose without transfusion, the dose will be decreased by one level at every 4 weeks. If tri-lineage is maintained within normal level for 4 consecutive weeks with 3 µg/kg without transfusion, AMG531 will be discontinued.

Normal level is defined as platelet counts $>50 \times 10^9/L$ and hemoglobin concentration >10.0 g/dL and neutrophil counts $>1.0 \times 10^9/L$.

While tapering, if platelet counts drop to less than $30 \times 10^9/L$, hemoglobin to less than 9.0 g/dL, or neutrophil counts to less than $0.5 \times 10^9/L$, the tapering has to be stopped and dose will be adjusted following section 6.1.3.2. If the study drug were discontinued, it will be resumed at a dose of 3 µg/kg and further adjusted in accordance with section 6.1.3.2. Tapering may be tried again at the discretion of investigator.

While tapering, if patient does not meet the criteria of further tapering but maintains steady stable response, the dose will be kept stable. During tapering, dose reduction should follow section 6.1.3.3, not 6.1.3.2. While discontinuation, if patient maintains the steady stable response, dosing will not be resumed

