Study duration of each subject in this study is specified as the period from the day of obtaining written informed consent through the end of examinations on completion of treatment (or withdrawal).

Observation and Examination Period

In this study, Week 1 (Day 1) is defined to be the day of initial administration of AMG531. Initial dose evaluation period is defined to be the period from Week 1 to Week 8, Extension period is the period from Week 9 to Week 52, and Long-term treatment period is the period from Week 53 to Week 156.

Aplastic Anemia with Refractory Thrombocytopenia

Aplastic anemia with thrombocytopenia defined as platelet count of $\leq 30 \times 10^9/L$ that does not respond to the immunosuppressive therapy (ATG + cyclosporine), or relapsed after having showed response.

Transfusion Independence

Achieving platelet or RBC transfusion free period of at least 8 consecutive weeks.

Tri-lineage response

Tri-lineage response is defined in those achieving platelet response, erythroid response, and neutrophil response all together.

Normal level

Normal level is defined as platelet counts $>50 \times 10^9/L$, hemoglobin concentration >10.0 g/dL, and neutrophil counts $>1.0 \times 10^9/L$

Stable response

Stable response is defined as platelet counts $\geq 30 \times 10^9/L$, hemoglobin concentration ≥ 9.0 g/dL, and neutrophil counts $\geq 0.5 \times 10^9/L$ maintained during dose tapering or discontinuation without transfusion

Cytogenetic abnormality

Any cytogenetic abnormalities newly emerged during or after the initiation of AMG531 treatment

PROTOCOL SYNOPSIS

I TITLE

A phase 2, Randomized, Open-Label, Parallel, Comparative, Dose-Finding Study to Evaluate the Efficacy and Safety of AMG531 in Aplastic Anemia (AA) Subjects with Thrombocytopenia Refractory to Immunosuppressive Therapy

[figure not shown]
II STUDY OBJECTIVES

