6.2 Concomitant medications and therapies

6.2.1 Concomitant medications and therapies

Throughout the study period, investigator may prescribe any concomitant medications or therapies deemed necessary to provide adequate supportive care except for those listed in section 6.2.2. Rescue medication is defined as any medication that is administered to raise platelet counts, hemoglobin concentration or neutrophil counts. Rescue medication should only be administered when subjects is at immediate risk except for the case of transfusion. Platelet and RBC transfusions will be allowed during the study period as clinically indicated. Platelet counts, hemoglobin concentration and neutrophil counts determined after administration of rescue medication suspected to affect its level will not be used for the efficacy assessment. For the platelet transfusion, only single donor platelet (SDP) transfusion will be allowed during the study period.

Iron chelator will be allowed during the study period as clinically indicated.

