6.2.2 Prohibited medications and therapies

While on study treatment, subjects are not permitted to receive any additional experimental medication or any therapy known or suspected to affect platelet production and AA from the time of enrollment throughout the study period. Examples of prohibited medications or therapies are follows;

- 1) Any investigational agents other than AMG531
- 2) TPO agonist other than AMG531

- 3) Other drugs to treat AA or symptoms associated with AA (e.g., immunosuppressive agents, cyclosporine, growth factors [For the case of G-CSF, its administration is only permitted as a rescue medication to treat infection, and will be prohibited for the purpose of treating AA])
- 4) Any medication known or suspected to affect platelet production
- 5) Hematopoietic stem cell transplantation

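### The taper and stop triggers in 6.1.3.3 exclude transfusion-supported runs but not neutrophil counts raised by permitted rescue G-CSF

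*Combined protocol and SAP*

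**What the plan says.** **Dosing rules (6.1.3.3; same rules in synopsis V-3).** The taper starts after a qualifying 8-week run: "If tri-lineage is maintained within normal level for 8-consecutive weeks with the same dose without transfusion". The stop rule asks for 4 consecutive weeks at normal level on 3 µg/kg and ends "without transfusion, AMG531 will be discontinued". Normal level means platelets >50 x10^9/L, hemoglobin >10.0 g/dL and ANC >1.0 x10^9/L. No condition is attached for rescue medication. A platelet count below 30, hemoglobin below 9.0 or ANC below 0.5 halts the taper or, if the drug is already stopped, restarts it.

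**G-CSF.** Section 6.2.2 bars G-CSF as treatment for AA, but "its administration is only permitted as a rescue medication to treat infection". Section 6.2.1 limits rescue further: "Rescue medication should only be administered when subjects is at immediate risk except for the case of transfusion".

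**Affected counts.** Section 6.2.1 says that platelet, hemoglobin and "neutrophil counts determined after administration of rescue medication suspected to affect its level will not be used for the efficacy assessment". Section 12.1.1 makes this specific for G-CSF by setting aside ANCs within 7 days, again for efficacy assessment.

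**What is reported.** Section 12.1.1.2 gives the proportions of subjects who reach normal level for 8 weeks, who begin the taper and who stop drug. Stopping after a transfusion-free 8-week run is also a secondary endpoint (3.3.1.2).

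**The concern.** Transfusion props up platelets and hemoglobin, and the triggers rule it out. The permitted agent that props up the third lineage is rescue G-CSF, and the triggers do not mention it. The plan recognises elsewhere that an ANC soon after G-CSF does not show what the subject's marrow is doing, but it applies that only when efficacy is assessed.

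The taper and stop steps are mandatory. During a taper, 6.1.3.3 directs dose reduction to its own rules rather than to the discretionary ones in 6.1.3.2, and section 15 allows deviations only for immediate hazard. An investigator who doubts an ANC taken a few days after G-CSF therefore has no clear written ground to wait. The subject concerned has just had an infection that needed rescue, which is a poor moment to cut or stop the drug on a supported count. Beginning the taper and stopping drug are dosing events, so setting the ANC aside at analysis does not remove the subject from those two counts.

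**Working it through.** The plan gives no figure on this point, so there is none to reproduce. The check has two parts: a comparison of the texts, and a count of how many scheduled ANCs one G-CSF episode can reach.

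**1. Texts side by side**

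| Rule | ANC condition | Support excluded |
|---|---|---|
| 8-week taper trigger (6.1.3.3, V-3) | >1.0 throughout | transfusion only |
| 4-week stop trigger (6.1.3.3, V-3) | >1.0 throughout | transfusion only |
| Efficacy assessment (6.2.1, 12.1.1) | any ANC used | rescue medication; G-CSF within 7 days |

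Nothing carries the third row into the first two. The protocol can write such a link: in the extension-period dosing rule (6.1.2), "If no platelet measurement is available due to the platelet transfusion", that week counts as no response.

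**2. Visits reached by one episode**

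Inputs: hematology is weekly while on drug, with ±3 days allowed (8.2.4); the window is 7 days (12.1.1). Assumptions: the window runs from the day after the first dose to 7 days after the last dose; a course, where given, lasts 5 days.

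Window length = (course days − 1) + 7.
- Single dose: 0 + 7 = 7 days.
- 5-day course: 4 + 7 = 11 days.

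Visits exactly 7 days apart:
- Any 7 consecutive days contain exactly one visit, so a single dose reaches 1 count on all 7 possible start days.
- 11 = 7 + 4, so a 5-day course reaches 2 counts on 4 of 7 start days and 1 count on the other 3.

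Share of the run:
- Taper: 1/8 = 12.5%; 2/8 = 25%.
- Stop: 1/4 = 25%; 2/4 = 50%.

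With the ±3-day allowance:
- Consecutive visits can be up to 7 + 6 = 13 days apart. That leaves 12 visit-free days, more than either window, so 0 counts is possible and the gap then does not arise.
- Three visits can fall as close as days 3, 7 and 11 (nominal days 0, 7 and 14 shifted by +3, 0 and −3), a span of 9 calendar days. This exceeds the 7-day window and fits the 11-day one. The range is therefore 0–2 for a single dose and 0–3 for a 5-day course.
- The extreme shares are 3/8 = 37.5% and 3/4 = 75%. If all whole-day shifts are equally likely and visits are at least 3 days apart, three counts occur in about 2% of 5-day courses.

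**3. When a decision changes**

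All of the following must hold: a scheduled ANC falls in the window and reads above 1.0; without G-CSF it would have been 1.0 or lower; platelets and hemoglobin are at normal level; and every other count in the run qualifies. The documents give neither the frequency of G-CSF use nor the size of the ANC rise, so the number of changed decisions cannot be computed.

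**The case against.** **Normal level may already be an efficacy term.** It is defined alongside the response terms and used in secondary endpoints, and 6.2.1 sits in the dosing chapter. Judging whether it is maintained could fairly be called an efficacy assessment. That reading is possible, but 6.1.3.3 restates normal level for dosing and names transfusion alone. Even on that reading, the text does not say whether an excluded week breaks the run or delays the decision, so sites could differ.

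**The event is rare and reversible.** Only 32 subjects are planned. Long-term entry needs a platelet response confirmed in Weeks 46–53, and G-CSF is confined to infection in a subject at immediate risk. A scheduled ANC of 1.0 or lower before the course already breaks the run. On exact visits, 6 or 7 of the 8 taper counts must still qualify unaided, and an ANC below 0.5 reverses course. All of this stands, and it keeps the point small.

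**The 6.1.2 comparison is loose.** That rule covers a missing platelet count and treats it as failure. It shows that the protocol writes such handling into dosing rules; it does not dictate the remedy here.

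**Stronger readings that do not hold.** A reader might extend the point to restarting drug: "While discontinuation, if patient maintains the steady stable response, dosing will not be resumed", and stable response is defined as "maintained during dose tapering or discontinuation without transfusion", also silent on G-CSF. But waiting for the next unaffected ANC would leave the subject off drug at the affected visit, exactly as now, and an ANC below 0.5 restarts drug either way. No dosing decision changes. A reader might also infer that the plan calls these ANCs unusable for dosing. It excludes them from efficacy assessment only.

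**Conclusion.** The point holds for the taper and stop triggers. Followed literally, a G-CSF-supported ANC above 1.0 counts toward cutting or stopping the drug, and the subject then enters the reported taper and discontinuation counts. The reach is 1 count for a single dose and 1 to 2 for a 5-day course on exact weekly visits, of 8 or 4; with the visit allowance it is 0 to 2 and 0 to 3. These figures rest on the assumed course length and on the window as defined above. They count exposed visits, not altered decisions, which are probably few. The effect is confined to long-term dosing and descriptive secondary endpoints. The Week 9 primary endpoint is not touched, and 12.1.1 already keeps affected ANCs out of efficacy assessment. This is a cheap improvement to the wording, not a flaw that threatens the trial's conclusions.

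**What to change.** Add to 6.1.3.3 and synopsis V-3:

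*An ANC >1.0 x10^9/L measured within 7 days after rescue G-CSF does not count toward the 8-week or 4-week normal-level run; the current dose is kept until the required number of ANCs outside that window has been met. An ANC ≤1.0 x10^9/L inside the window still breaks the run, and an ANC <0.5 x10^9/L still stops the taper or restarts drug.*

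The second sentence matters. A rule that ignored every in-window ANC would be looser than the present text, because a value of, say, 0.7 despite G-CSF breaks the run now and should go on doing so. Keeping the dose meanwhile fits the existing instruction to hold it when a stable subject does not qualify for further tapering.

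In 12.1.1.2, count normal-level attainment and discontinuation as *without transfusion and without reliance on an ANC within 7 days of rescue G-CSF*.

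Cost: a few sentences, with no new data or visits, since 6.2.3 already records concomitant medication with its duration and justification. For a subject given G-CSF, the taper or stop is delayed by about 1–2 weekly visits (7–14 days), or up to 3 visits with the ±3-day allowance. The discontinuation proportion may come out slightly less favourable.
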